4.4.5. Selection and Timing of Dose for Each Subject

Each subject is to be randomly assigned to a study group which will define the number and timing of 2013 and/or 2017 A/H7N9 vaccinations. The first vaccination for all subjects takes place on the day of randomization and will include vaccination with AS03 adjuvanted 2013 A/H7N9 IIV (Groups 1,2,3) or AS03 adjuvanted 2017 A/H7N9 IIV (Groups 4,5,6). The second vaccination of 2017 A/H7N9 IIV takes place approximately 21 days after the first vaccination for Groups 1 and 4 (protocol defined window of 21-28 days post first vaccination), and approximately 120 days after the first vaccination for Groups 2, 3, 5, and 6 (protocol defined window of 113-134 days post first vaccination).

4.4.6. Blinding

This is a partially blinded clinical trial. Subjects, site investigators, and study personnel performing any study-related assessments following study vaccine administration to the subject are partially blinded (blinded to vaccine antigen and dosage and unblinded to vaccine administration interval). Laboratory personnel performing HAI and Neut antibody assays will receive serum specimens blinded to subject ID number and specimen visit number.

The randomization scheme will be generated by the SDCC and provided to unblinded study personnel (i.e., research pharmacists performing study vaccination preparations and unblinded study vaccine administrators) at the participating VTEU sites.

The unblinded study vaccine administrator is a study personnel member credentialed to administer vaccines and may also participate in dose preparation but will not be involved in study-related assessments or have subject contact for data collection following study vaccine administration to the subject.

The Data and Safety Monitoring Board (DSMB) may receive data in aggregate and presented by study groups. The DSMB may also be provided with expected and observed rates of the expected AEs in an unblinded fashion and may request the treatment assignment be unblinded for an individual subject if required for safety assessment. The DSMB will review grouped and unblinded data in the closed session only.

4.4.7. Prior and Concomitant Therapy

Administration of any medications, therapies, or vaccines (including prescription and over-the-counter drugs as well as herbals, vitamins, and supplements) from 60 days prior to study vaccination through 21 days post final vaccination will be solicited from the participant during screening, enrollment, and follow-up. Any reported prior therapies from up to 30 days prior to vaccination through 21 days post final vaccination will be recorded in the appropriate data collection form.

Use of concomitant medications is allowed prior to and during the trial with the exception of medications and therapies that might interfere with the evaluation of the investigational product. Medications in this category include the prohibited medication per the Subject Exclusion Criteria (protocol Section 5.1.2). In addition, the site principal investigator or appropriate sub-investigator may identify other medications that should not be used due to a risk to subject safety or assessment of reactogenicity and immunogenicity.

4.4.8. Treatment Compliance

All subjects are to receive two vaccinations of study product administered in the clinic based on study group assignment.

4.5. Immunogenicity and Safety Variables

See [Table 2](#), [Table 3](#), [Table 4](#), and [Table 5](#) for schedules of study procedures by study groups.

4.5.1. Safety Variables

Safety will be assessed by the frequency and severity of:

1. SAEs occurring from the time of the first study vaccination through approximately 12 months after the last study vaccination.
2. Solicited AEs – reactogenicity events occurring from the time of each study vaccination through 7 days after each study vaccination:

- Injection site reactions including pruritus, ecchymosis, erythema, induration (hardness)/edema (swelling), pain, and tenderness.
 - Systemic reactions including fever, feverishness, fatigue, malaise, myalgia, arthralgia, headache, and nausea.
3. Clinical safety laboratory AEs occurring from the time of each study vaccination through approximately 7 days after each study vaccination. Parameters to be evaluated include white blood cells (WBC), hemoglobin (Hgb), platelets (PLT), alanine aminotransferase (ALT), total bilirubin (T. Bili), and creatinine (Cr).
 4. Unsolicited AEs – non-serious AEs occurring from the time of each study vaccination through approximately 21 days after each study vaccination.
 5. MAAEs, including NOCMCs, and PIMMCs occurring from the time of the first study vaccination through approximately 12 months after the last study vaccination.

Grading scales for injection site and systemic solicited reactions, vital signs, and clinical laboratory parameters are provided in [Table 10](#), [Table 11](#), [Table 12](#), and [Table 13](#).

For each unsolicited AE experienced, the subject will be asked if he/she had received medical attention, defined as hospitalization, an emergency room visit or an otherwise unscheduled visit to or from medical personnel for any reason. AEs characterized by such unscheduled medical care will be designated as MAAEs.

NOCMCs are defined as any new ICD-10 diagnosis (10th revision of the International Statistical Classification of Diseases and Related Health Problems) that is applied to the subject during the course of the study, after receipt of the study agent, that is expected to continue for at least 3 months and requires continued health care intervention.

PIMMCs constitute a group of AEs that includes diseases which are clearly autoimmune in etiology and other inflammatory and/or neurologic disorders which may or may not have autoimmune etiologies. For a list of PIMMCs currently in effect, refer to protocol Appendix B.

4.5.2. Immunogenicity Variables

Individual HAI and Neut results will be reported by the central immunology laboratory for the homologous 2013 A/H7N9 vaccine strain and 2017 A/H7N9 vaccine strain. Assay results are reported as a reciprocal titer with values of 10×2^k , where $k=0, 1, 2$, etc. The lower limit of detection (LLOD) for the HAI and Neut assays is 1:10; values below the limit of detection are imputed for analysis as one-half the limit of detection ($10/2 = 5$). For analysis, the geometric mean (calculated on natural log scale) of repeated results for each sample will be computed and used as the response for all subsequent calculations. The variation arising from multiple measurements for an individual at a single time point is not used in subsequent calculations. See Section 3.3 for definitions of derived variables for the analysis of HAI and Neut data. HAI and Neut data will be uploaded into the SDCC's electronic data capture system.

Frequency of strain-specific (2013 and 2017 A/H7N9) plasmablasts (IgA, IgG and IgM ASCs) will be characterized by the local laboratory using freshly collected PBMCs. A single frequency value will be reported, with a LLOD of 6 and an ULOD of 8000. Values below the LOD will be reported as one-half the LLOD ($6/2 = 3$). Values above the ULOD will be assessed for accuracy.

A plan for receipt of exploratory data will be determined with the assaying laboratories and documented in the SAP addendum.

The assay to determine the influenza virus N9 Neuraminidase (NA) antibody response to vaccination is under development. An addendum to the SAP will be generated to outline the planned analyses when assay development is complete and after receiving confirmation of this plan from DMID.

5. SAMPLE SIZE CONSIDERATIONS

This study is planned to enroll up to 180 subjects. This study is not designed to test a formal null hypothesis. Rather, it is intended to obtain sufficient data to obtain meaningful estimates of the immune response and to uncover any safety issues that occur at a sufficiently high rate that they might be observed in a study of this size. As such, the type I error rate, $\alpha = 0.05$, is not adjusted for multiple comparisons. While this study is not designed to test any specific null hypothesis, the following tables illustrate the precision and power that is available for select estimates and comparisons of interest.

[Table 6](#) indicates the probability of observing one or more safety events, such as solicited injection site or systemic reactogenicity events or an unsolicited non-serious AE of a particular type for a single study group ($N = 30$), or in the trial as a whole ($N=180$).

Binomial confidence intervals (CI) are widest (have the least precision) when the response rate is 50%.

[Table 7](#) is presented to indicate the worst-case scenario for precision of observed exact (Clopper-Pearson) binomial confidence intervals.

[Table 8](#) illustrates the minimum detectable differences in the proportion of subjects responding (e.g. attaining seroconversion or a titer $\geq 1:40$) between any two study groups ($N=30$) using a two-sided Likelihood Ratio Test and $\alpha = 0.05$. It is assumed that up to 10% of subjects ($N=3$) will be excluded from the per protocol analysis. Seroconversion rates of 10% to 50% are considered.

6. GENERAL STATISTICAL CONSIDERATIONS

6.1. General Principles

Unless otherwise specified, continuous variables will be summarized using the following descriptive statistics: n (non-missing sample size), mean and/or geometric mean (as appropriate), standard deviation, median, maximum and minimum. The frequency and percentages (based on the non-missing sample size) of observed levels will be reported for all categorical measures. In general, all data will be listed, sorted by study vaccination and subject, and when appropriate by visit number within subject. All summary tables will be structured with a column for each study group in the following order:

- Group 1: 2013 3.75 + AS03 / 2017 3.75 + AS03 (D1-D22)
- Group 2: 2013 3.75 + AS03 / 2017 3.75 + AS03 (D1-D121)
- Group 3: 2013 3.75 + AS03 / 2017 15 (D1-D121)
- Group 4: 2017 3.75 + AS03 / 2013 3.75 + AS03 (D1-D22)
- Group 5: 2017 3.75 + AS03 / 2017 3.75 + AS03 (D1-D121)
- Group 6: 2017 3.75 + AS03 / 2017 15 (D1-D121)

All tables will be annotated with the total population size relevant to that table/treatment, including any missing observations.

6.2. Timing of Analyses

6.2.1. CSR

Clinical, safety and reactogenicity data through approximately 180 days after the last study vaccination will represent the primary clinical database for this trial. Once the last subject completes the visit that occurs approximately 180 days after the last study vaccination and all HAI and Neut results are received and clinical data lock has occurred, a "topline" subset of the immunogenicity and safety tables will be provided to DMID on an expedited timeline. These analyses may be made available to the sponsor for planning subsequent trials and to the lead PI for publication. These analyses will not be used to make any decisions concerning the conduct of this trial. As it is anticipated that subjects may remain in long-term safety and immunogenicity follow-up at the time of these analyses, blinded site investigators and DMID Medical Monitors not involved in the analysis, publication or clinical study report (CSR) preparation will be responsible for assessing SAEs and MAAEs, including NOCMCs and PIMMCs, until all subjects have completed the final follow-up visit. All analyses of data included in the topline tables for early release will be considered the final analysis of these data, and also included in the final CSR.

Tables and figures to be included in the topline set are indicated with the symbol * in the title.

Analysis of exploratory immunogenicity endpoints, including cellular immunology and additional serological assays, may be performed and released as the data are available from the research laboratories. Any such analyses would be considered the final analysis for the endpoint and included in the CSR.

The final CSR will be completed after the last subject's last visit is completed, and the final clinical database, including all long-term safety follow-up data, is cleaned, monitored and locked. Additional exploratory

immunogenicity endpoint data not available at the time of CSR preparation may be included in an addendum to the CSR.

6.3. Analysis Populations

6.3.1. Safety Population

The Safety Analysis population includes all subjects who received at least one study vaccination.

6.3.2. Modified Intent-to-Treat (mITT) Population

The modified Intent-to-treat (mITT) population includes all subjects who received at least one study vaccination and contributed both pre- and at least one post-study vaccination venous blood samples for immunogenicity testing (HAI or Neut antibody assays) for which valid results were reported. For analyses using the mITT population, subjects will be grouped based on randomized study group. Subject inclusion in mITT analyses will be considered individually for each assay.

6.3.3. Per Protocol Population

The per protocol (PP) population includes all subjects in the mITT subset with the following exclusions:

- Data from all available visits for subjects found to be ineligible at baseline.
- Data from all visits subsequent to major protocol deviations, such as:
 - Second study vaccination not received,
 - Second study vaccination received out of window,
 - Receipt of non-study licensed, live vaccine within 30 days before or after each study vaccination,
 - Receipt of non-study licensed, inactivated vaccine within 14 days before or after each study vaccination,
 - Receipt of immunosuppressive therapy (e.g., corticosteroids) within 30 days before or after each study vaccination.
- Data from any visit that occurs out of window by more than one day. However, use exact window for visits that occur either 1 day or 3 days post study vaccinations:
 - Visit 2 data collected before 1 day or after 2 days post first study vaccination.
 - Visit 3 data collected before 3 days or after 4 days post first study vaccination.
 - Visit 4 data collected before 5 days or after 10 days post first study vaccination.
 - Visit 5 data collected before 12 days or after 16 days post first study vaccination.
 - Visit 6 data collected before 20 days or after 29 days post first study vaccination.
 - Visit 7 data collected before 1 day or after 2 days post second study vaccination for study groups 1 and 4.

-
- Visit 8
 - Data collected before 3 days or after 4 days post second study vaccination for study groups 1 and 4.
 - Data collected before 112 days or after 135 days post first study vaccination for study groups 2, 3, 5, and 6.
 - Visit 9
 - Data collected before 5 days or after 10 days post second study vaccination for study groups 1 and 4.
 - Data collected before 1 day or after 2 days post second study vaccination for study groups 2, 3, 5, and 6.
 - Visit 10
 - Data collected before 12 days or after 16 days post second study vaccination for study groups 1 and 4.
 - Data collected before 3 days or after 4 days post second study vaccination for study groups 2, 3, 5, and 6.
 - Visit 11
 - Data collected before 20 days or after 29 days post second study vaccination for study groups 1 and 4.
 - Data collected before 5 days or after 10 days post second study vaccination for study groups 2, 3, 5, and 6.
 - Visit 12
 - Data collected before 53 days or after 67 days post second study vaccination for study groups 1 and 4.
 - Data collected before 12 days or after 16 days post second study vaccination for study groups 2, 3, 5, and 6.
 - Visit 13
 - Data collected before 75 days or after 105 days post second study vaccination for study groups 1 and 4.
 - Data collected before 20 days or after 29 days post second study vaccination for study groups 2, 3, 5, and 6.
 - Visit 15
 - Data collected before 165 days or after 195 days post second study vaccination for study groups 1 and 4.
 - Data collected before 75 days or after 105 days post second study vaccination for study groups 2, 3, 5, and 6.

- Visit 17 data collected before 165 days or after 195 days post second study vaccination for study groups 2, 3, 5, and 6.

For analyses using the PP population, subjects will be grouped based on study vaccinations received. Analyses will be conducted using the PP population only if 10% or more of subjects are excluded from a primary or secondary analysis timepoint.

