15. Have been hospitalized for psychiatric illness, history of suicide attempt, or confinement for danger to self or others within 10 years prior to study vaccination.
16. Have taken oral or parenteral (including intra-articular) corticosteroids of any dose within 30 days prior to study vaccination.
17. Have taken high-dose inhaled corticosteroids⁸ within 30 days prior to each study vaccination.

⁸High-dose defined as per age as using inhaled high-dose per reference chart in the National Heart, Lung and Blood Institute Guidelines for the Diagnosis and Management of Asthma (EPR-3) or other lists published in UPTODATE.

18. Received a licensed, live vaccine within 30 days prior to the first study vaccination, or plan to receive a licensed, live vaccine within 30 days before or after each study vaccination.
19. Received or plan to receive a licensed, inactivated vaccine (excluding all licensed, seasonal IIVs) within 14 days before or after each study vaccination.
20. Received or plan to receive a licensed, seasonal IIV within 21 days before or after each study vaccination.
21. Received immunoglobulin or other blood products (except Rho D immunoglobulin) within 90 days prior to each study vaccination.
22. Received an experimental agent⁹ within 30 days prior to the first study vaccination or expect to receive an experimental agent¹⁰ during the trial-reporting period¹¹.

⁹Including vaccine, drug, biologic, device, blood product, or medication.

¹⁰Other than from participation in this trial.

¹¹Approximately 12 months after the last study vaccination.

23. Are participating or plan to participate in another clinical trial with an interventional agent¹² that will be received during the trial-reporting period¹³.

¹²Including licensed or unlicensed vaccine, drug, biologic, device, blood product, or medication.

¹³Approximately 12 months after the last study vaccination.

24. Received or plan to receive an influenza A/H7 vaccine¹⁴ or have a history of influenza A/H7 subtype infection.

¹⁴And assigned to a treatment arm receiving influenza A/H7 vaccine, i.e., does not apply to documented placebo recipients.

25. Had substantial direct contact¹⁵ with live or freshly slaughtered poultry or pigeons while in mainland China within the past five years.

¹⁵Substantial direct contact is defined as visited a poultry farm and/or a live poultry market.

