7.2. Protocol Deviations

A summary of subject-specific protocol deviations will be presented by the deviation category and deviation type, and study group for all enrolled subjects ([Table 9](#)). Major deviations that will be reviewed for possible exclusion of immunogenicity results from the PP population include deviations related to eligibility/enrollment, treatment administration schedule, follow-up visit schedule, and receipt of exclusionary vaccines or medications. All subject-specific protocol deviations and non-subject-specific protocol deviations will be included in [Listing 3](#) and [Listing 4](#).

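### The listed per-protocol exclusions give all inactivated vaccines a 14-day window, but the protocol bars seasonal IIV within 21 days, so receipt on days 15 to 21 has no stated handling

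*SAP*

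**What the plan says.** Protocol 5.1.2 treats inactivated vaccines in two parts. Criterion 19 covers all but seasonal influenza vaccine: "Received or plan to receive a licensed, inactivated vaccine (excluding all licensed, seasonal IIVs) within 14 days before or after each study vaccination". Criterion 20 gives seasonal IIV a longer window: "Received or plan to receive a licensed, seasonal IIV within 21 days before or after each study vaccination".

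The PP definition does not keep that split. SAP 6.3.3 and Protocol 11.6.1 carry the same single line: "Receipt of non-study licensed, inactivated vaccine within 14 days before or after each study vaccination". It has no carve-out for seasonal IIV, and no other line mentions seasonal IIV.

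Three other statements bear on how the line works:

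- The list is introduced as examples: "Data from all visits subsequent to major protocol deviations, such as".
- A separate line removes "Data from all available visits for subjects found to be ineligible at baseline".
- SAP 7.2 provides for review: "Major deviations that will be reviewed for possible exclusion of immunogenicity results from the PP population include deviations related to eligibility/enrollment". The same sentence goes on to include "receipt of exclusionary vaccines or medications", without a number of days.

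**The concern.** The protocol separates seasonal IIV from other inactivated vaccines and gives it the longer window. The PP list collapses the two into the shorter one. Its neighbours do follow their criteria: the live-vaccine line uses 30 days, as criterion 18 does, and the corticosteroid line uses 30 days, as criterion 16 does. Only the seasonal IIV window has been lost.

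Seasonal IIV is itself an inactivated vaccine, so the only PP window that covers it is 14 days. Someone programming from the list would treat receipt on day 17 as acceptable. Someone reviewing deviations against criterion 20 could remove the same subject's later data. The SAP does not say which is intended.

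This matters because SAP 8.1 uses PP to show how sensitive the immunogenicity results are to adherence. The plan also treats seasonal influenza vaccination as relevant to these endpoints: prior receipt stratifies randomization, and receipt is a covariate in SAP 8.3.2. Classification also feeds the roughly 10% exclusion threshold that decides whether PP displays are produced (SAP 6.3.3 and 8).

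**Working it through.** The plan states no figure on this point to reproduce. The check counts the days that criterion 20 bars and the listed PP rules do not reach.

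**Inputs**

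- Barred window for seasonal IIV: 21 days either side of each dose (Protocol 5.1.2, criterion 20).
- Listed PP window: 14 days either side of each dose (SAP 6.3.3, Protocol 11.6.1).
- Dose interval *d*, Groups 1 and 4: 21 to 28 days (SAP 4.4.5, "protocol defined window of 21-28 days post first vaccination").
- Dose interval *d*, Groups 2, 3, 5 and 6: 113 to 134 days (SAP 4.4.5).
- Primary draw: Day 22 with a +7 day window after dose 2, that is 21 to 28 days after it (Protocol 8.2.12).
- Day 22 draw after dose 1 in the 4-month arms: also 21 to 28 days after the dose (Protocol 8.2.5).

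**Rule.** Put dose 1 at day 0 and dose 2 at day *d*. Receipt on day *t* is barred but unlisted when the nearer dose is 15 to 21 days away: 15 ≤ min(|*t*|, |*t* − *d*|) ≤ 21.

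**Groups 1 and 4**

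- Days 15 to 21 after dose 1 lie between 21 − 21 = 0 and 28 − 15 = 13 days before dose 2.
- Days 15 to 21 before dose 2 lie between 21 − 21 = 0 and 28 − 15 = 13 days after dose 1.
- Both sets fall inside the 14-day line, so there is no between-dose gap once dose 2 is given in window.

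**Groups 2, 3, 5 and 6**

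- Days 15 to 21 after dose 1 are uncovered: 7 days.
- Days 15 to 21 before dose 2 are uncovered: 7 days. The earliest is day 113 − 21 = 92, so the two sets do not overlap.

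| Groups | Before dose 1 | Between doses | After dose 2 | Total less the days before dose 1 |
|---|---|---|---|---|
| 1, 4 | 7 | 0 | 7 | 0 + 7 = 7 |
| 2, 3, 5, 6 | 7 | 14 | 7 | 14 + 7 = 21 |

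The 7 days before dose 1 are dropped from the total because receipt then makes the subject ineligible at baseline, which the PP definition already handles. The result is the same for every interval in each window.

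**Which uncovered days can reach a blood draw**

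- After dose 2, all arms: vaccine on days 15 to 21 can precede the primary draw by 21 − 21 = 0 to 28 − 15 = 13 days.
- After dose 1, 4-month arms: the same arithmetic applies to the Day 22 draw, a secondary time point.
- Before dose 2, 4-month arms: eligibility is rechecked and non-study influenza vaccines are asked about at the dose-2 visit (Protocol 8.2.7). A subject who no longer meets eligibility is not given dose 2 (Protocol 5.2.3), and a missed second dose is a listed PP deviation.

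The recheck cannot act on receipt after dose 2. For receipt after dose 1 it comes only once the Day 22 sample has been taken, and the missed-dose rule removes later visits, not that one.

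**Scale.** One subject is 1/27 = 3.7% of the planned PP arm size in Protocol 11.4.3. How many would be affected cannot be derived from the documents.

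**After the fix.** With a listed 21-day window for seasonal IIV, the uncovered days are 0 in every group.

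**The case against.** The strongest reply is that nothing in the text keeps these subjects in PP. The list gives examples, and SAP 7.2 sends receipt of barred vaccines to review without a 14-day limit. SAP Table 15 has an exclusion reason for non-study vaccination, also without a window. That stands. A reader might infer that recipients on days 15 to 21 remain in PP; the documents support only that their handling is unspecified. Review without a stated window still leaves membership to judgment in each case.

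A reader might also infer a 7-day gap on each side of every dose in all arms. The dose intervals and the baseline-ineligibility line rule that out, and the dose-2 recheck narrows the between-dose part further.

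Nor does the SAP depart from the protocol's PP definition, since both use the same line. The conflict is between that shared definition and criterion 20. A threshold for a major deviation need not equal an eligibility window, so 14 days could be deliberate. However, neither document says so, and the neighbouring lines do follow their criteria.

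It is also fair that the consequences are bounded. The primary population is mITT (SAP 8 and 8.1). It would go too far to say that every regression runs on PP: SAP 8.3.2 names PP for the immunogenicity models, but SAP 8.3 makes this depend on more than 10% of subjects having data excluded, and the solicited-event models use the Safety population. The 2018-2019 seasonal vaccine covariate offers partial adjustment, but it counts receipt only up to dose 2 and so misses the days ahead of the primary draw.

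**Conclusion.** The point holds as a minor inconsistency in the PP definition. Seasonal IIV given 15 to 21 days from a study dose breaches criterion 20, matches no listed PP deviation, and is left to case review with no stated window. The uncovered days are 7 in Groups 1 and 4 and 21 in Groups 2, 3, 5 and 6, so the gap differs by dosing interval, which is one of the modeled treatment factors in SAP 8.3.2. The exposure that matters most is receipt after dose 2 ahead of the primary draw and, in the 4-month arms, receipt after dose 1 ahead of the Day 22 draw.

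The counts assume that dose 2 is given within its window and that receipt before dose 1 is treated as baseline ineligibility. No bias in any estimate has been shown. The primary mITT summaries are not affected.

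**What to change.** Before unblinding, reconcile the PP list with criterion 20 in SAP 6.3.3: add receipt of licensed seasonal IIV within 21 days before or after each study vaccination, and limit the 14-day line to other inactivated vaccines. Make the same change in Protocol 11.6.1 at its next amendment; because the protocol's list is illustrative, the SAP clarification need not wait for it. If the 14-day window was meant to cover seasonal IIV, the SAP should instead say that days 15 to 21 are deliberately not a major deviation.

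No new data are needed, since receipt of non-study influenza vaccines is already collected through about 180 days after the last dose (Protocol 6.6). The cost is one line of text and possibly a few more PP exclusions.
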